Primary outcome: Screening rate in the intervention group vs. control group after 6 months.

Secondary outcomes:

A) Complete screening rate in both groups, which is defined as completion of the entire screening strategy. For colonoscopy, this requires cecal intubation and an adequate bowel preparation. For individuals who took Septin9 and FIT, positive results must be followed by a colonoscopy with cecal intubation and adequate bowel preparation.

B) Among individuals in the intervention group who had a positive blood test, proportion who completed a follow-up colonoscopy within 6 months.

C) Endoscopic and pathologic findings among individuals in the intervention group who had a diagnostic colonoscopy.

Aim #2: *To survey screen-resistant patients to understand their beliefs and attitudes about CRC screening and testing options.* Both intervention and controls groups will be invited to complete a brief questionnaire. Questionnaire questions are shown in the Table and are adapted from a previous study that offered both the blood test and FIT to patients who had refused screening colonoscopy.⁴ All response options will be presented in a multiple-choice format. The full questionnaire is shown in the Appendix.

Primary outcome: Demographic and health-related predictors of accepting the blood test in the intervention group.

Secondary outcomes:

A) Proportion of both groups who answered that they would be willing to take a blood test for colorectal cancer screening

B) The most commonly cited advantages of a blood test compared to colonoscopy and stool test in both groups

C) The most commonly cited reasons for not taking the blood test in the intervention group. In an exploratory analysis, we will stratify results by race/ethnicity, self-reported health, frequency of healthcare access, and self-perceived risk of CRC.

Table. Select Questionnaire Questions

Demographics
What is your age?
What is your race?
What is your ethnicity?
Health status and medical history
How would you rate your overall health?
How many visits have you had with your primary care doctor in the past year?
What do you think is your own risk of getting colorectal cancer?
Colorectal cancer testing
Have you ever had a colonoscopy? If so, when?
Have you ever had a stool-based test? If so, when?

PROTOCOL TITLE: Assessing the effect of offering a blood-based colorectal cancer screening test

Why did you decide not to do a colonoscopy when offered in the past 6 months?

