Participants who are randomized to the blood test arm will undergo phlebotomy, which will be performed by the study research assistant. The blood sample will be temporarily stored on-site and then transported to an off-site commercial laboratory to run the assay.

Clinical outcomes for both the intervention and control group participants will be measured as a secondary outcome. This includes timing and result of a screening colonoscopy or FIT for individuals in the controls group as well as diagnostic colonoscopy for participants who had a positive blood test.

PROTOCOL TITLE: Assessing the effect of offering a blood-based colorectal cancer screening test

10) Data and Specimen Banking

Blood specimens for individuals in the intervention group will be assayed but not stored. No data other than what is described in the sections above will be stored.

11) Data Management

Blood specimens will be transported and assayed by an outside commercial laboratory. Result will then be uploaded to the electronic medical record.

All personnel who will be working on this project will have completed the necessary CITI and TMS training for research involving patient data. Data will be collected from the electronic medical record, which only individuals credentialed by the VA can access using password-protected accounts. All data collected will be compiled in a password-protected spreadsheet, and sharing of data will be restricted to the study personnel listed on the proposal using VA email. After data has been collected from the electronic health record, the data will be de-identified prior to analysis.

Data Analysis

Aim 1: Screening rates in the intervention vs. control groups will be compared using the chi-squared or Fisher's exact test. Clinical outcomes of individuals who took the blood test will be reported as descriptive statistics.

Aim 2: We will use a multivariable logistic regression model to assess demographic and health-related predictors of accepting the blood test. We will perform descriptive statistics to assess the secondary outcomes. Results for secondary outcomes will also be reported stratified by race/ethnicity, self-reported health, frequency of healthcare access, and self-perceived risk of CRC.

Sample Size Calculations

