Aim 1: Two prior studies that have measured uptake of the Septin9 blood test have found very high rates of 84% and 99%, respectively.^{4,5} The study that found 84% uptake involved patients who had previously declined colonoscopy and were subsequently given a choice between the blood test and FIT. Since our study population has previously declined both colonoscopy and FIT, their uptake of the blood test will likely be lower. We estimate that uptake in our population will be 50% and will power our study to detect a 15% absolute difference in screening rate. With alpha = 0.05 and 80% power, the required sample size in each group is 170. To account for drop-out, we will include 180 patients in each group.

Aim 2: Assuming a 50% uptake in the intervention group of 170 individuals, there will be an estimated 85 individuals who take the blood test. We will select variables with the strongest association with blood test completion on bivariate analysis, which will be entered into the final multivariable logistic regression model. The number of variables in the final model will be limited to ensure that there are at least 10 events per variable, which is the conventional minimum standard to preserve model validity.¹⁶

12) Provisions to Monitor the Data to Ensure the Safety of Subjects

We believe this study poses no more than Minimal Risk to study participants, and therefore there are no plans to establish a data monitoring committee. However, any unexpected adverse events will be reported immediately to the PI, who will report to the IRB on an ad-hoc basis.

PROTOCOL TITLE: Assessing the effect of offering a blood-based colorectal cancer screening test

13) Withdrawal of Subjects

There are no anticipated circumstances under which subjects will be withdrawn from the research without their consent. Participants may choose to withdraw from the study at any point by giving notification to the study team. Patients who withdraw from the study will no longer be tracked in the electronic medical record after the time of withdrawal.

14) Risks to Subjects

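### Choosing Aim 2 predictors by strongest bivariate association and estimating them on the same participants overstates weak or moderate effects and flags null predictors too often, if any candidates are discarded

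*Combined protocol and SAP*

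**What the plan says.** Section 8 (Study Endpoints, Aim 2) defines the outcome: "Primary outcome: Demographic and health-related predictors of accepting the blood test in the intervention group". The Data Analysis paragraph gives the method: "We will use a multivariable logistic regression model to assess demographic and health-related predictors of accepting the blood test".

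The Sample Size Calculations paragraph for Aim 2 says how the model is built. The expected count is: "Assuming a 50% uptake in the intervention group of 170 individuals, there will be an estimated 85 individuals who take the blood test". The variables are chosen as follows: "We will select variables with the strongest association with blood test completion on bivariate analysis". Those chosen then make up the final model. Model size is restricted: "The number of variables in the final model will be limited to ensure that there are at least 10 events per variable".

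None of these places lists the candidate predictors, describes a validation sample, bootstrap or shrinkage, or calls the model exploratory. In section 8 the word exploratory is attached to a stratified analysis among the secondary outcomes, not to this model. The questionnaire items shown there stand under "Table. Select Questionnaire Questions", with the note: "The full questionnaire is shown in the Appendix".

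**The concern.** Ranking variables by their observed association and keeping the top ones favours those whose association happens to be large in this sample. Re-estimating them on the same participants carries that chance excess into the reported odds ratios and intervals. The limit of 10 events per variable restrains overfitting in the final model, but it takes no account of how many variables were tried.

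At stake is the Aim 2 primary outcome, the description of who accepts a blood test. Some reported predictors could be products of selection, and some real but weak ones could look stronger than they are. The randomised Aim 1 comparison of screening rates does not use this model.

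**Working it through.** **The plan's own figures.** 170 × 0.50 = 85 takers, as stated. The 170 is the Aim 1 group size; it reproduces for 50% vs 35%, two-sided alpha 0.05 (sidedness assumed) and 80% power. The cap is 85 / 10 = 8.5, so at most 8 variables. At 30% uptake it is 51 / 10 = 5.1, so 5.

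**Number of candidates.** Not stated in the available text. The table in section 8 shows six demographic or health items: age, race, ethnicity, overall health, primary care visits and perceived risk. It is a selection. It lists seven items before the stool-test question, which is number 14 in the questionnaire, so 13 − 7 = 6 earlier items are not in it. Some of those may be eligibility questions, because section 4 uses questionnaire data for exclusions. Candidate counts above six are therefore assumptions.

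**Null predictors, by arithmetic.** With m independent null candidates, about 0.05 × m have an interval excluding 1. Keeping the k strongest keeps nearly all of these, so the share among kept variables is about 5% × m / k.

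**Null predictors, by simulation.** n = 170, independent normal predictors ranked by absolute correlation with the outcome, top k refitted by logistic regression, Wald 95% intervals (level assumed; the plan gives none for Aim 2), 6,000 data sets per row. The last two columns give the share of intervals excluding 1.

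| Kept of tried | Takers | 5% × m / k | Selected | Pre-specified, same size |
|---|---|---|---|---|
| 6 of 6 | 85 | 5.0% | 5.0% | 5.0% |
| 5 of 6 | 51 | 6.0% | 6.3% | 5.4% |
| 4 of 6 | 85 | 7.5% | 7.3% | 5.0% |
| 3 of 6 | 85 | 10.0% | 9.7% | 4.9% |
| 8 of 10 | 85 | 6.3% | 6.6% | 5.3% |
| 8 of 12 | 85 | 7.5% | 7.9% | 5.3% |
| 8 of 20 | 85 | 12.5% | 12.9% | 5.2% |

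A separate run of 3,000 data sets gave 5.5% (6 of 6), 7.0% (4 of 6), 7.4% (8 of 12) and 13.2% (8 of 20).

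**One real predictor among nulls.** 85 takers expected, 4,000 data sets per cell. Mean odds ratio when kept, against the pre-specified mean, and interval coverage:

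| Kept of tried | True OR 1.2 per SD | Coverage (selected vs pre-specified) | True OR 1.3 per SD | Coverage (selected) |
|---|---|---|---|---|
| 4 of 6 | 1.256 vs 1.211 | 94.0% vs 95.0% | 1.352 vs 1.320 | 95.6% |
| 8 of 12 | 1.257 vs 1.206 | 94.2% vs 95.3% | 1.349 vs 1.315 | 95.5% |
| 8 of 20 | 1.316 vs 1.216 | 93.2% vs 94.9% | 1.394 vs 1.321 | 95.4% |

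**A strong predictor.** With a true OR of 2.0 per SD, alongside two predictors of OR 1.3 and nulls, the variable was always kept. The average OR (exponentiated mean log OR) was 2.09 with 8 of 8 and 2.10 with 8 of 20. The small excess over 2.0 is ordinary small-sample bias; selection adds nothing to it.

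**The case against.** The strongest reply is that selection may hardly operate. The six visible items fit under the cap of 8 at planned uptake if each takes one parameter, and entering all six gives no inflation. The larger figures rest on assumed candidate counts. Aim 2 is framed as understanding beliefs and attitudes, with no significance level or decision attached to the predictors. This stands as a limit on the size. It does not remove the point: a rule for taking the strongest variables has no purpose unless some are discarded, and the result is still the Aim 2 primary outcome.

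A reader might infer three stronger things that are not supported.

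- That every reported odds ratio will be exaggerated. Strong predictors that are always selected are not affected, and coverage for weak real predictors falls by only about 1–2 points.
- That dropping real predictors is peculiar to this method. A real OR of 1.2 is dropped in 18% (4 of 6), 20% (8 of 12) and 35% (8 of 20) of data sets. A list of the same size chosen without knowing which predictor is real would omit it in 2/6 = 33%, 4/12 = 33% and 12/20 = 60%.
- That the cap is miscounted as planned. At 50% uptake takers and non-takers are equal. Only above that, and only if events means takers, is it too loose: at 60%, 102 takers would allow 10 variables while 68 non-takers support 6.

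**Conclusion.** The concern holds conditionally. The plan states a rule that selects and estimates on the same participants, without correction or exploratory label, and its cap does not protect against this. If fewer variables are kept than tried, weak or moderate odds ratios are overstated on average, and intervals for null predictors exclude 1 too often: about 7% instead of 5% with the best 4 of 6, and about 7–13% with 8 kept of an assumed 12 to 20. If all candidates are entered, there is no inflation.

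These sizes assume independent continuous predictors, complete data on 170 people and conventional 95% intervals; they are illustrative. The documents do not establish how many candidates will be tried, so they do not show that the larger figures apply. Aim 1 is unaffected. The change is worth making because it concerns a primary outcome and costs little.

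**What to change.** Replace the bivariate screening step with a pre-specified, ordered list of demographic and health-related predictors, with categories collapsed in advance and counted in model parameters. One illustration is age (1), race/ethnicity (2), self-rated health (1), primary care visits (1) and perceived risk (1), 6 in all; content and order are for the investigators.

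Enter the list in order, up to one tenth of the smaller of takers and non-takers with usable data. That number may be below 170, because sections 21 and 23 make the questionnaire voluntary. For example, 100 complete responders at 50% uptake give 50 / 10 = 5 parameters. Report all coefficients with 95% confidence intervals, stated as not adjusted for multiplicity: with 6 independent null predictors the chance of at least one interval excluding 1 is 1 − 0.95^6 = 26.5%.

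If more candidates or data-driven selection are wanted, there are two options.

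- Enter all candidates in a Firth-type penalised logistic model with profile-likelihood intervals. Under the null this gave 4.7% with 12 or 20 predictors at 85 takers, and 4.7% with 6 at 51 takers. It was not checked with real effects.
- Keep the selection, label the model exploratory, and report bootstrap inclusion frequencies and optimism-corrected (shrunken) odds ratios, repeating the selection in each resample. This was not simulated here.

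The cost is one paragraph of analysis wording and no new data. The downside is less freedom to explore extra predictors. If the team already intends to enter every candidate, the edit only records that.

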Patients will be informed of the potential risks as part of the informed consent process. All efforts will be made to ensure patient confidentiality and assurance of HIPAA compliance. Participant data will be de-identified using a protocol-specific unique code that will be used for all further data management. A list matching the patient medical record number to the protocol specific unique code will be maintained in a password-protected file in the PI's private drive on the VA network. There will be no data entry or interpretation outside of the VA NY Harbor Health Care System. The names of the patients will not be revealed in written reports or publications detailing the research findings.

21) Provisions to Protect the Privacy Interests of Subjects

The study team will take every possible precaution to protect the privacy of study participants. Only study team members who have been trained by the PI will be allowed to access patient data. Participants data will be de-identified for analysis and only aggregate data will be presented for publication. In addition, participants will not be required to answer any questionnaire question that may make him/her not at ease.

22) Compensation for Research-Related Injury

N/A

23) Consent Process

We are requesting waiver of HIPAA and informed consent for the purpose of screening patients who are eligible for participating in the study. For the control arm, we are requesting waiver of HIPAA and informed consent to access their medical record and determine whether they undergo a colonoscopy for FIT within 6 months of the initial invitation letter. For participants in the intervention arm who elect to undergo the blood test, written informed consent and HIPAA authorization will be obtained onsite prior to phlebotomy. All patients will also be invited to participate in a short anonymous questionnaire by mail and if needed, by phone. A one-page description of the questionnaire and how to contact the research team will be provided in the mailing and reiterated in the phone call. However, we are requesting waiver of documentation of consent for the anonymous questionnaire.

24) Drugs or Devices

N/A

PROTOCOL TITLE: Assessing the effect of offering a blood-based colorectal cancer screening test

REFERENCES

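### Section 13 ends record tracking at any withdrawal, so some 6-month screening outcomes that could be read from the record will be unknown, and the plan has no rule for counting these patients

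*Combined protocol and SAP*

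**What the plan says.** - **Withdrawal (section 13).** "Participants may choose to withdraw from the study at any point by giving notification to the study team". The consequence is stated without exception: "Patients who withdraw from the study will no longer be tracked in the electronic medical record after the time of withdrawal". No lesser option is described, such as ending contact while the record check continues.
- **Outcome (section 8, Aim 1).** "Primary outcome: Screening rate in the intervention group vs. control group after 6 months". Secondary outcome A is completion of the whole screening strategy. Secondary outcome B is follow-up colonoscopy within 6 months after a positive blood test.
- **Data source (section 11).** "Data will be collected from the electronic medical record". Blood test results are also uploaded there. For controls, section 23 describes the outcome check as a look in the medical record, under a waiver, for colonoscopy or FIT in the 6 months after the letter.
- **Order of events (sections 6 and 9).** Patients are randomised first. The letter, telephone call and questionnaire follow in both arms, and the intervention letter adds the blood test offer.
- **Consent (section 23).** "For participants in the intervention arm who elect to undergo the blood test, written informed consent and HIPAA authorization will be obtained onsite prior to" (the blood draw).
- **Analysis (section 11, Data Analysis).** "Screening rates in the intervention vs. control groups will be compared using the chi-squared" or Fisher's exact test. There is no analysis population, no denominator for withdrawers and no missing-outcome rule.
- **Sample size (section 11).** "With alpha = 0.05 and 80% power, the required sample size in each group is 170", and then "To account for drop-out, we will include 180 patients in each group". No drop-out rate is given.

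**The concern.** Where outcomes need a study visit, losing withdrawers is often unavoidable. Here it is not. Once a patient is randomised, the screening outcome can be read from the record whether or not that patient ever answers the study team. The loss comes from the rule in section 13.

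All withdrawals happen after randomisation, in a population that has already declined two tests. A request to be left alone is foreseeable, and it is plausibly related to not being screened. If such patients leave the denominator, the observed screening rate rises in whichever arm loses more of them. If they stay in, the analyst needs a rule for their value, and none is given. A choice made after the data are seen is open to challenge.

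Outcome B is exposed in another way. A patient with a positive test who withdraws before colonoscopy can no longer be followed, and that patient's failure to follow through is what outcome B is meant to measure.

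**Working it through.** **1. The plan's own figure.** Inputs from section 11: 50% uptake, a 15-point difference (taken as 50% versus 35%), alpha 0.05 (two-sided assumed) and 80% power. With p̄ = 0.425:

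n = [1.960·√(2 × 0.425 × 0.575) + 0.842·√(0.50 × 0.50 + 0.35 × 0.65)]² / 0.15² = 3.8095 / 0.0225 = 169.3, rounded up to **170**. This matches.

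The allowance is 180 − 170 = 10 per arm, or 10/180 = 5.6%.

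**2. Whose primary outcome is lost.** Tracking stops only from withdrawal onward, so a test already recorded still counts. The unknown outcomes belong to patients unscreened at withdrawal.

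**3. Effect of dropping unscreened withdrawers.** The documents give no counts, so the plan's allowance of 10 serves as an illustration. The difference is x₁/(180 − w₁) − x₀/(180 − w₀), where w is the number dropped from each arm. P-values are from the uncorrected chi-squared test.

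| Dropped (intervention, control) | Comparison | Difference (points) | p |
|---|---|---|---|
| 0, 0 | 90/180 vs 63/180 | 15.0 | 0.004 |
| 10, 10 | 90/170 vs 63/170 | 15.9 | 0.003 |
| 10, 0 | 90/170 vs 63/180 | 17.9 | 0.0007 |
| 0, 10 | 90/180 vs 63/170 | 12.9 | 0.015 |
| 10, 0 with no true effect | 63/170 vs 63/180 | 2.1 | 0.69 |

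Nearer the threshold, 80/180 versus 63/180 gives p = 0.067. Dropping 10 from the intervention arm only (80/170 versus 63/180) gives p = 0.022. Dropping 10 from each arm (80/170 versus 63/170) gives p = 0.062. The crossing therefore needs unequal losses.

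**4. Bounds with equal losses.** Suppose 10 per arm are unknown and the observed results are 85/170 and 59/170 (35% of 170 is 59.5).

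- Least favourable: 85/180 − (59 + 10)/180 = 16/180 = 8.9 points, p = 0.088.
- Most favourable: (85 + 10)/180 − 59/180 = 36/180 = 20.0 points, p = 0.0001.

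Taking 60 instead of 59 gives 8.3 points (p = 0.110) and 19.4 points.

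**5. Outcome B.** Assume 90 tests (50% of 180). The specificities of 79% and 82% in section 3 imply about 90 × 0.21 = 18.9 and 90 × 0.18 = 16.2 positives from patients without cancer. With an assumed 12 colonoscopies among 19 positives, the proportion is 12/19 = 63%. If 3 of the non-completers withdraw and are dropped, it becomes 12/16 = 75%.

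**6. Power under the proposed counting rule.** With every outcome known for 180 per arm, power for 50% versus 35% is 82.4%. Now suppose 10 per arm refuse record review and count as unscreened, and the other 170 are screened at the planned rates. The rates become 85/180 = 47.2% and 59.5/180 = 33.1%, and power is 78.5%. If all 10 are in the intervention arm, the difference is 47.2 − 35.0 = 12.2 points and power is 65.5%.

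**The case against.** **Ending record review at withdrawal may be a deliberate privacy term**, above all where access rests on a waiver. Consent pages are not among the documents, so tiered choices may exist there. This stands in part. A patient's right to refuse record review must be kept, but section 13 as written offers nothing short of it, and the absence of a counting rule does not depend on the consent form.

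**Section 13 speaks of withdrawing from the study, not of declining a call or questionnaire.** This is correct. The questionnaire is a separate anonymous invitation, and its questions may be left unanswered (sections 21 and 23). How staff would classify a patient who says only that they want no more contact is unstated, which is a reason to define it.

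**A reader might infer that withdrawal will be commoner in the intervention arm and so inflate the effect.** The documents do not support this for the primary outcome. Intervention patients who sign consent do so just before the blood draw, so nearly all have in effect been screened before they would withdraw. Everyone else has similar contact in both arms apart from the blood test offer.

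**A reader might also infer that the 10 extra patients per arm are the section 13 withdrawers, to be excluded.** The sample size text makes no such link and prescribes no exclusion, so a complete-case analysis is only one possible outcome of the plan's silence.

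**The one-arm scenarios are extremes.** This too stands. At the planned effect the result stays significant in every dropping scenario in the table, and with no true effect the spurious difference is 2.1 points.

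**Conclusion.** The point holds in a limited form. Following section 13 makes outcomes unknown after randomisation although they could be read without the patient's participation, and the plan does not say how those patients are counted.

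Neither the direction nor the size of any bias can be settled from the documents. With the plan's 10-per-arm allowance as an assumed number of withdrawals, all unscreened and dropped, a 15.0-point difference reads 15.9 with equal losses, 17.9 if only the intervention arm loses patients, and 12.9 if only the control arm does. If nothing is assumed about 10 unknown outcomes per arm, the 85/170 versus 59/170 result is compatible with 8.9 to 20.0 points, and the lower bound is not significant. Fewer withdrawals shrink all of these effects. Outcome B is more fragile because its denominator is small, but it is a descriptive secondary outcome.

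Severity is minor to moderate and confidence is moderate. The rule itself is plain in the text, but how often it will apply is unknown.

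**What to change.** **In section 13, define two choices:** (a) no further contact or study procedures, with the 6-month record check continuing where the consent or waiver permits; (b) refusal of further record review as well. Record the choice, the arm and the date. Section 23 should also state the basis for the 6-month record check in intervention patients who do not take the blood test. At present it names a waiver for controls and consent for those who take the test.

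**In the Data Analysis text, state that:**
- all randomised patients are analysed in their assigned arm;
- type (b) patients count as not screened unless screening was recorded before withdrawal;
- withdrawals are reported by arm and type;
- one best/worst-case sensitivity analysis is done, as in step 4 of the working;
- outcomes A and B follow the same denominator rule, so a patient with a positive test who withdraws stays in the denominator of B.

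**Cost.** An IRB amendment to wording and one extra question at withdrawal, with no added patients. Observed rates will be slightly lower, and some power is lost if many choose (b): 78.5% with 10 per arm and 65.5% with 10 in the intervention arm only, against 82.4% with complete data. The section 13 change has to be made before follow-up, because an outcome left unread under the present rule can be imputed or bounded at analysis but not observed.

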The proposed study is a randomized controlled trial that will 1) assess the uptake of a CRC screening blood test among patients who have declined both colonoscopy and FIT in the previous 6 months, including diagnostic evaluation of positive results and 2) survey patients about their beliefs and attitudes regarding CRC screening and testing options. All participants will be primary care patients at the VA NY Harbor Health Care System. Based on a recent internal audit, there were 1502 patients who had at least one primary care visit from August 2016 through August 2017 and were not up to date with CRC screening. Up to date CRC screening is defined as either 1) a colonoscopy within the past 10 years or 2) FIT within the past year. We will perform an updated CRC screening audit at the beginning of the study to obtain the entire pool of eligible patients who are not up to date with screening. Eligible patients will then be randomized 1:1 to either an intervention group or a control group. All patients will receive a letter noting that they are not up to date on screening and encouraging them to contact a study number if they choose to screen with colonoscopy or FIT. Patients who call will speak to a research assistant who is trained in patient navigation and can facilitate referrals for colonoscopy or FIT. Following the sequential testing approach, letters addressed to the intervention group will also include an option to participate in the blood test, with instructions to call the study number to schedule the blood draw. In addition to the letter, both groups will also receive a follow-up telephone call that reiterates information in the letter. The research assistant will make and receive all calls using a standard script. All patients will also be asked to complete a questionnaire about their beliefs and attitudes regarding CRC screening (see Appendix). The questionnaire will be mailed with the invitation letter and will also be administered over the telephone by the research assistant. The study team will notify patients and their primary care physicians of blood test results and will facilitate a colonoscopy referral for those with positive tests. Primary care physicians will not be asked to notify the patients or make the colonoscopy referral because most will not have adequate knowledge of the Septin9 test to provide appropriate patient education.

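### Section 23 requests 6-month colonoscopy/FIT record access for controls but not for intervention patients who do not take the blood test, although the primary outcome needs both whole arms

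*Combined protocol and SAP*

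**What the plan says.** Section 23 (Consent Process) makes four provisions.

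1. For all patients, a "waiver of HIPAA and informed consent for the purpose of screening patients who are eligible for participating in the study". Its stated purpose is eligibility, not outcomes.
2. For controls: "For the control arm, we are requesting waiver of HIPAA and informed consent to access their medical record". The purpose is to find colonoscopy or FIT within 6 months of the initial invitation letter.
3. "For participants in the intervention arm who elect to undergo the blood test, written informed consent and HIPAA authorization will be obtained onsite", before phlebotomy.
4. "All patients will also be invited to participate in a short anonymous questionnaire by mail and if needed, by phone", with a waiver of documentation of consent.

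Section 8 (Study Endpoints) gives the primary outcome as "Screening rate in the intervention group vs. control group after 6 months". The first secondary outcome is "Complete screening rate in both groups, which is defined as completion of the entire screening strategy".

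Sections 6 and 9 send every patient, in either arm, a letter "encouraging them to contact a study number if they choose to screen with colonoscopy or FIT". The intervention letter adds the blood test.

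Section 9 also states: "Clinical outcomes for both the intervention and control group participants will be measured as a secondary outcome". The list that follows names screening colonoscopy or FIT for controls, and diagnostic colonoscopy for patients with a positive blood test. Screening colonoscopy or FIT in the intervention arm is not named.

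Section 11 takes data from the electronic medical record without limit by arm. Section 13 says that patients who withdraw stop being tracked there, which presupposes that the others are.

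**The concern.** An intervention patient who does not take the blood test is randomised, receives the same colonoscopy/FIT letter and telephone call as a control, and belongs in the denominator of the intervention screening rate. None of the four provisions in Section 23 covers reading that patient's 6-month record.

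If access follows that text, a colonoscopy or FIT in a control is found by chart review, while the same event in one of these intervention patients is found only if it comes to light some other way. Ascertainment of the primary outcome and of the complete screening rate would then differ by arm, and no later analysis can restore events that nobody was permitted to look up.

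The other contacts do not close the gap. The questionnaire is described as anonymous and is mailed with the invitation, before the 6-month window has run. Calls with the research assistant would reveal some events but do not establish completion.

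**Working it through.** **Coverage of outcome access in Section 23**

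| Group | Basis for reading 6-month colonoscopy/FIT outcomes |
|---|---|
| Controls | Waiver requested |
| Intervention, blood test taken | Written consent and HIPAA authorization |
| Intervention, blood test not taken | None stated |

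**The plan's own sample size.** The Sample Size Calculations (Section 11) give 170 per group for a 15-point difference with alpha 0.05 and 80% power. Taking 50% vs 35%, two-sided, with pooled variance:

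n = [1.960 × √(2 × 0.425 × 0.575) + 0.842 × √(0.50 × 0.50 + 0.35 × 0.65)]² / 0.15², which rounds up to 170.

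This reproduces the stated figure. The change proposed below does not alter it.

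**Size of the uncovered group.** Inputs: n = 180 per arm (Section 5) and blood-test uptake u = 0.50 (Section 11). The group is 180 × (1 − 0.50) = 90 patients, or 85 of 170 on the Aim 2 figures.

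**Understatement.** Let r be the share of these patients who have a colonoscopy or FIT within 6 months, and c the share of those events that become known anyway. Events not seen are counted as unscreened. The documents give neither r nor c; both are assumed.

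- Patients missed = 90 × r × (1 − c)
- Understatement of the intervention rate, and so of the difference = 0.50 × r × (1 − c)

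This understatement does not depend on the control rate. To show it against a difference, the table also assumes that controls screen at the same rate r. The true difference is then (0.50 + 0.50r) − r, and the difference observed with nothing captured is 0.50 − r.

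| Assumed r | Missed (c = 0) | Understatement (c = 0) | Understatement (c = 0.5) | True difference | Observed difference (c = 0) |
|---|---|---|---|---|---|
| 1% | 0.9 | 0.5 points | 0.25 points | 49.5 | 49.0 |
| 5% | 4.5 | 2.5 points | 1.25 points | 47.5 | 45.0 |
| 10% | 9 | 5 points | 2.5 points | 45.0 | 40.0 |
| 20% (extreme) | 18 | 10 points | 5 points | 40.0 | 30.0 |

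**Effect on the test.** By exact enumeration at 180 per arm, power of the uncorrected two-sided chi-squared test stays above 99.9% in every row, even with nothing captured.

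**The case against.** The strongest reply is that the intent is plain. Section 8 defines both outcomes for both groups, and Sections 11 and 13 imply that everyone is followed in the record. The control-arm sentence in Section 23 is loosely drafted, so an omission is the likelier explanation. A separate waiver application may cover all patients. This stands as far as it goes: a reader might infer that these records would go unread, and the documents do not show that. But Sections 11 and 13 presuppose tracking without requesting access, and Section 9 repeats the control-only listing. The plan still contradicts itself on how its primary outcome is obtained.

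A second reply is that the rates should be low. Eligible patients declined both tests within 6 months, and the protocol's introduction argues that the pool willing to have either test is saturated. The research assistant also navigates referrals for callers and telephones both groups. This too stands. It favours the low end of the range and makes 20% with nothing captured an extreme case.

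Two stronger readings are tempting.

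- *Patients without a blood test are dropped and the effect is doubled.* Nothing in the plan suggests this. The Sample Size Calculations keep them in the denominator (85 takers among 170), and the Aim 2 model needs them as non-acceptors.
- *The trial loses power.* Subtracting 2.5 or 5 points from 50% vs 35% would cut power at 180 per group from 82.4% to 67.5% or 49.1%. However, the plan's 50% is blood-test uptake, which is fully captured. Missed events come on top of it, not out of it, so at that uptake the documents do not support a loss of power.

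**Conclusion.** The point holds as a conflict between the access requested in Section 23, with the matching list in Section 9, and the both-arm outcomes in Section 8. Whether access was in fact limited cannot be determined from the documents.

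If Section 23 is followed as written, the bias runs against the intervention: its screening rate and the difference are understated. The range is 0.5 to 5 points for assumed rates of 1% to 10% with nothing captured, and 0.25 to 2.5 points if half the events are known through study calls. These figures rest on the plan's 50% uptake, on assumed colonoscopy/FIT rates, and on counting unseen events as unscreened. The conclusion of the significance test at 50% uptake is not in question. What suffers is the size of the effect, which is the figure the study is meant to supply.

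**What to change.** In Section 23, request the outcome-ascertainment waiver (colonoscopy and FIT within 6 months of the initial invitation letter) for all randomised patients in both arms. Keep written consent and HIPAA authorization for the blood draw.

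In Section 9, state that screening colonoscopy, FIT, blood test and diagnostic colonoscopy are ascertained in both arms by the same chart review over the same 6-month window, and that every patient is analysed in the arm to which they were randomised.

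The cost is about one sentence in each section, a slightly broader minimal-risk waiver request, and about 90 more charts to review. The sample size stays at 180 per group. If wider access has already been granted, the edit only brings the protocol into line with it.
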